If this application involves the use of a HUD "humanitarian" device: describe whether the use is for "on-label" clinical patient care, "off-label" clinical patient care, and/or research (collecting safety and/or effectiveness data).

This quality improvement research study aims to improve the utilization of genetic counseling and testing among providers at Olympic Medical Center (OMC) who are caring for their cancer patients in a rural and underserved area. SCCA will coach the OMC providers to offer eligible patients genetic counseling and testing in order to increase access and help the OMC site meet genetic recommendations and guidelines. Specifically, this study aims to (1) review and develop OMC's clinical operations workflow to identify cancer patients who meets criteria for genetic counseling and testing; (2) measure uptake of genetic testing; and (3) document clinical and patient reported outcomes following genetic test results.

1.6 Study design. Provide a one-sentence description of the general study design and/or type of methodology.

Your answer will help HSD in assigning applications to reviewers and in managing workload. Examples: a longitudinal observational study; a double-blind, placebo-controlled randomized study; ethnographic interviews; web scraping from a convenience sample of blogs; medical record review; coordinating center for a multi-site study.

This is a quality improvement research study in which SCCA will provide coaching to OMC providers to offer genetic counseling and testing in order to address current gaps in caring for their high-risk patients.

1.7 Intent. Check all the descriptors that apply to your activity. You must place an "X" in at least one box.

This question is essential for ensuring that your application is correctly reviewed. Please read each option carefully.

Descriptor

- 1. Class project or other activity whose purpose is to provide an educational experience for the researcher (for example, to learn about the process or methods of doing research).
- 2. Part of an institution, organization, or program's own internal operational monitoring.

Document Date & Version

11/15/2019

Version 2.2

#2003

[name]

5/4/2020

Version 1

Page 3 of 46

3. Improve the quality of service provided by a specific institution, organization, or program.

4. Designed to expand the knowledge base of a scientific discipline or other scholarly field of study, and produce results that:

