5 PROCEDURES

5.1 Study procedures.

Using lay language, provide a complete description of the study procedures, including the sequence, intervention or manipulation (if any), drug dosing information (if any), use of records, time required, and setting/location. If it is available: Upload a study flow sheet or table to [Zipline](#).

For studies comparing standards of care: It is important to accurately identify the research procedures. See UW IRB [POLICY: Risks of Harm from Standard Care](#) and the draft guidance from the federal Office of Human Research Protections, ["Guidance on Disclosing Reasonably Foreseeable Risks in Research Evaluating Standards of Care"](#); October 20, 2014.

This quality improvement research study is designed in two phases, each phase is done over a 3-month period for a total study duration of 6 months. The SCCA study team will be enrolling eligible OMC providers who will handle all patient interaction and communication.

Phase 1: The first phase does not involve intervention; OMC will be following their existing processes. OMC will gather identified data on the patient's clinic diagnosis and stage, pathology report features, and treatment options for patients with the above diagnose and offer patients the option to fill out a standardized Family History Questionnaire (FHQ) on the day of their initial visit if they decide to do so. The FHQ will be offered as part of clinical care up to the discretion of the OMC providers. OMC will also gather de-identified data on the number of patients seen with a diagnosis of breast, ovarian, prostate, colon, and pancreatic cancer. The above data will then be sent to the study's research coordinator at SCCA (through secure email) which will be stored in a secured J-Drive folder within the SCCA network. The research coordinator will randomly assign all identified patient data to a unique participant ID before distributing to SCCA subject matter experts (cancer geneticist and/or genetic counselor) for review. From OMC's collected data, SCCA subject matter experts will measure how many patients met NCCN criteria for testing how many patients were referred to genetic counseling and how many either had a test online or were seen at UWMC and the SCCA for a genetic evaluation.

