Phase 2: The second phase involves a tiered intervention in which SCCA subject matter experts will coach the OMC providers to provide guidance on providing genetic counseling and testing to their patients. Involvement in this study does not dictate how the OMC providers carry out clinical care, so it is up to the OMC providers to decide whether or not to implement the coaching in their practice. First, patients and their families fill out the standardized FHQ before their initial appointment, which will be sent via email by the team at OMC. OMC will gather the same patient information described in Phase 1 which will then be sent directly to the study's research coordinator at SCCA, where the research coordinator will follow the same data storage, participant ID assignment, and distribution processes as in Phase 1. SCCA subject matter experts would then review this information with the OMC providers at bi-monthly virtual conferences before patients come for their initial visit at OMC. For patients who meet NCCN criteria, the oncology team at OMC would include in their initial visit workflow to discuss importance of cancer risk assessment and offer genetic testing. For the patients with a more complicated history, the OMC team would offer a referral to the SCCA for a complete cancer risk assessment evaluation.

At the end of phase 2, SCCA subject matter experts will measure how many patients met NCCN criteria for testing how many patients were referred to genetic counseling and how many either had a test online or were seen at UWMC and the SCCA for a genetic evaluation. This data will then be compared with phase 1 data to measure the effectiveness of SCCA's coaching for OMC's providers as well as quality improvement of their processes.

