a.3. Explain which results will not be offered to subjects and provide the rationale for not offering these results.

Reasons not to offer the results might include:

- *There are serious questions regarding validity or reliability*
- *Returning the results has the potential to cause bias*
- *There are insufficient resources to communicate the results effectively and appropriately*
- *Knowledge of the result could cause psychosocial harm to subjects*

b. What is the plan (if any) for offering subjects any results that are not clinically actionable?

Examples: non-actionable genetic results, clinical tests in the normal range, experimental and/or uncertain results.

	No
	Yes

→ If yes, explain which results will be offered to subjects and provide the rationale for offering these results.

c. Describe the validity and reliability of any results that will be offered to subjects.

The IRB will consider evidence of validity such as studies demonstrating diagnostic, prognostic, or predictive value, use of confirmatory testing, and quality management systems.

The results that will be offered to the OMC provider subjects will be reliable due to the consistent, uniform processes in data collection and recommendation that will be followed throughout the entire course of this study. The results will be valid because the reporting of the numbers of patients meeting criteria, referrals for genetic counseling/testing, completed genetics appointments, and genetic testing results, will be recorded and tracked by the same research coordinator.

d. Describe the process for communicating results to subjects and facilitating understanding of the results. In the description, include who will approach the participant with regard to the offer of results, who will communicate the result (if different), the circumstances, timing, and communication methods that will be used.

Results will be communicated to the OMC provider subjects at the end of phase 1 and phase 2. The SCCA study team and subjects will meet to discuss the number of patients seen who were eligible for genetic testing, number of those patients who were referred for genetic counseling/testing, the number of those patients who complete a genetics appointment, and the number of those patients who chose to undergo genetic testing. The OMC provider subjects will also be sent this data for their review in order to assess their current clinic processes.

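### Section 5.1 judges coaching on three unranked raw counts: one measures eligibility, none isolates the testing uptake of Aim 2, and nothing says which count decides

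*Protocol*

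**What the plan says.** Protocol 5.1 defines the measures once for each phase. For Phase 1 the first count reads: "From OMC's collected data, SCCA subject matter experts will measure how many patients met NCCN criteria for testing". The section words its second and third counts in this way: "how many patients were referred to genetic counseling and how many either had a test online or were seen at UWMC and the SCCA". The same three counts are taken at the end of Phase 2. The section then states its only effectiveness comparison: "This data will then be compared with phase 1 data to measure the effectiveness of SCCA's coaching for OMC's providers".

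Three other places bear on it:

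- Section 1.5 lists three aims. The second is to "measure uptake of genetic testing". It is not called primary.
- Section 10.10.d describes feedback to the providers after each phase. It starts from patients eligible for testing, then gives those referred, then "the number of those patients who complete a genetics appointment, and the number of those patients who chose to undergo genetic testing". Appointment and testing are separate there; in 5.1 they are merged.
- Section 2.7 gives 60/120 patients per phase as a maximum, with no calculation behind it.

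The document states no test, alpha, success threshold, denominator or order among the counts.

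**The concern.** One claim, that coaching was effective, rests on three numbers of different kinds.

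- **Met NCCN criteria** describes the patients and how well their history was recorded. It does not describe what providers did. In Phase 1 the family history questionnaire is optional, offered on the visit day at the providers' discretion. In Phase 2 it is emailed and filled out beforehand. Section 5.14 says the questionnaire serves to identify eligible patients, so fuller capture alone can raise this count.
- **Referred** need not rise if coaching works. In Phase 2 the local team offers testing itself to patients who meet criteria, and the SCCA referral is for the more complicated histories. Local testing could rise while referrals stay flat.
- **Tested or seen** adds two events together. A rise could be all appointments and no extra tests, so it does not answer Aim 2.

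If the counts disagree, 5.1 does not say what is concluded. A reader could then rest the effectiveness claim on whichever count rose, including the eligibility count, when referral and testing had not changed.

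**Working it through.** The plan gives no sample-size or error-rate figure to reproduce. The check has two parts.

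**1. What a capture change does to the counts.** These are illustrative figures. Take 60 patients per phase with the same true mix. Assume 40% are recognised as meeting criteria in Phase 1 and 50% in Phase 2, because more family history is on file. Hold referrals at 12 in both phases.

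- Met criteria: 60 × 0.40 = 24, then 60 × 0.50 = 30. This is a rise of 6 with no change in care.
- Referred among those meeting criteria: 12/24 = 50%, then 12/30 = 40%. This is an apparent fall.
- Referred among all patients: 12/60 = 20% in both phases.

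The raw eligibility count rises, the proportion among eligible patients falls, and the proportion among all patients is unchanged, although provider behaviour is the same. This is why the fix needs a second denominator.

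**2. How often chance alone gives a rise.** The document states no alpha, so one-sided 2.5% per count is assumed, since only an upward result can be read as success. It states no rates either. Assumed ranges are 40% to 60% eligible, 30% to 50% of those referred, and 50% to 70% of those tested or seen. Rates are identical in both phases.

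Model: eligible e ~ Bin(n, pe), referred r ~ Bin(e, pr), tested or seen t ~ Bin(r, pt), drawn independently for each phase.

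Test for counts x1 (Phase 1) and x2 (Phase 2): p = (x1 + x2)/(2n) and z = (x2 − x1)/n ÷ √(2p(1−p)/n), upward if z > 1.96. For the eligible-patient version, each phase's e replaces n and only referred and tested-or-seen are tested.

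Reference values for independent tests: 1 − 0.975³ = 7.3% for three, and 1 − 0.975² = 4.9% for two. Nested counts are correlated, so they should fall below these.

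Results with n = 60 per phase and 400,000 simulated null studies per row:

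| pe / pr / pt | Any of three counts upward | Either of two, among eligible |
|---|---|---|
| 0.40 / 0.30 / 0.50 | 6.1% | 4.4% |
| 0.50 / 0.40 / 0.60 | 6.2% | 4.3% |
| 0.60 / 0.50 / 0.70 | 6.0% | 4.2% |
| 0.40 / 0.50 / 0.70 | 5.5% | 4.2% |

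A single count was upward in 2.3% to 2.8%. Three other mixes inside the same ranges gave 6.0% to 6.4% for the three counts and 4.0% to 4.6% for the two. The quoted ranges, about 5.5% to 6.3% and about 4.2% to 4.4%, are therefore good to a few tenths of a point. With n = 120 the four rows give 5.7% to 6.4% and 4.2% to 4.4%, so the reading of 60/120 does not matter.

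Read by direction only, in the four rows at n = 60, at least one count is higher in Phase 2 in 66% to 70% of null studies, against 42% to 46% for any one count. One count rises while another falls in 33% to 40%.

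**The case against.** Section 5.1 answers a form question that asks for lay language, and the study calls itself a pilot and quality improvement research. Tests, alpha and multiplicity rules are commonly left to a statistical analysis plan, which is not shown. **This stands:** their absence is not the finding. It does not cover what 5.1 does state, which is an effectiveness comparison resting on three specific counts that do not match Aim 2.

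A reader might infer a false-positive rate of roughly 12% to 16%, as for three or four two-sided 5% tests. The documents do not support that. They state no test. About half of the two-sided events would be significant falls, which nobody would read as success. The counts are also nested, so the independent-test value (1 − 0.95³ = 14.3% for three) is too high.

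A reader might also take 10.10.d as a competing effectiveness analysis with four contrasts. It is feedback to providers after each phase and makes no between-phase claim. It matters only because its list differs from that in 5.1.

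The direction-only figures are weak evidence. They count a one-patient difference as a rise, and even a single named count rises in over 40% of null studies.

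Disagreement between steps of a care pathway is useful in quality improvement, because it shows where patients drop out. **This stands**, and it is a reason to keep reporting every step. Coaching also targets what providers offer, while testing depends on patients' choice, so choosing testing as the main measure is a judgement. Aim 2 supports that judgement but does not dictate it.

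**Conclusion.** The point holds in a limited form. As written, 5.1 can support a conclusion about coaching from an eligibility count that the Phase 2 questionnaire process may itself raise, or from a combined count that does not isolate testing uptake. It does not say which count decides when they differ.

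The chance component is modest. It is about 5.5% to 6.3% for at least one false upward result among the three counts, against a nominal 2.5%, and about 4.2% to 4.4% for the two outcome counts among eligible patients. These figures rest on an assumed one-sided 2.5% level, the assumed rates and no true change; none of the three comes from the document. They show the scale of an undefined decision rule and do not establish an alpha breach. The mismatch with Aim 2 and the difference in family-history capture do not depend on these assumptions, although the size of any capture effect is unknown. The change should be made but does not block the study.

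**What to change.** In 5.1, replace the general comparison of the Phase 2 data with Phase 1 by the following:

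1. **Main contrast, tied to Aim 2:** the Phase 2 minus Phase 1 difference in the proportion of patients meeting NCCN criteria who complete genetic testing, with its 95% confidence interval. The main conclusion about coaching rests on this.
2. **Descriptive process measures:** met criteria, referred and appointment completed, reported for each phase.
3. **Second denominator:** the same testing contrast over all patients seen with an eligible diagnosis, because family-history capture differs between phases and affects who is counted as meeting criteria.
4. **One list:** use the same steps in 5.1 and 10.10.d, with testing separate from being seen.

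Make the change before Phase 1 results are tabulated, since 10.10.d shares them at the end of that phase.

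The cost is wording. Section 10.10.c says the coordinator already tracks criteria met, referrals, completed appointments and testing results, and 5.1 already collects the number of patients seen by diagnosis. The small downside is that a rise in referral alone can no longer be presented as the main evidence that coaching worked.

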5.2 Recordings. Does the research involve creating audio or video recordings?

	No	→ If no, go to question 5.3 .						
	Yes	→ If yes, describe what will be recorded (if not already described in 5.1) and answer question a.						

a. Before recording, will consent for being recorded be obtained from subjects and any other individuals who may be recorded?
 

	No	→ If no, email [contact] before submitting this application in Zipline. In the email, include a brief description of the research and a note that individuals will be recorded without their advance consent.	

	Yes		

				No	→ If no, email [contact] before submitting this application in Zipline. In the email, include a brief description of the research and a note that individuals will be recorded without their advance consent.		Yes	
	No	→ If no, email [contact] before submitting this application in Zipline. In the email, include a brief description of the research and a note that individuals will be recorded without their advance consent.						
	Yes							

5.3 MRI scans. Will any subjects have a Magnetic Resonance Imaging (MRI) scan as part of the study procedures?

This means scans that are performed solely for research purposes or clinical scans that are modified for research purposes (for example, using a gadolinium-based contrast agent when it is not required for clinical reasons).

	No	→ If no, go to question 5.4 .
-------------------------------------	-----------	---

Yes → If yes, answer questions a through c.

a. Describe the MRI scan(s). Specifically:

- What is the purpose of the scan(s)? *Examples: obtain research data; safety assessment associated with a research procedure.*
- Which subjects will receive an MRI scan?
- Describe the minimum and maximum number of scans per subject, and over what time period the scans will occur. *For example: all subjects will undergo two MRI scans, six months apart.*

b. Use of gadolinium. Will any of the MRI scans involve the use of a gadolinium-based contrast agent (GBCA?)

No

Yes

→ If yes, which agents will be used? *Check all that apply.*

	Brand Name	Generic Name	Chemical Structure
	Dotarem	Gadoterate meglumine	Macrocyclic
	Eovist / Primovist	Gadoxetate disodium	Linear
	Gadavist	Gadobutro	Macrocyclic
	Magnevist	Gadpentetate dimeglumine	Linear
	MultiHance	Gadobenate dimeglumine	Linear
	Omniscan	Gadodiamide	Linear
	OptiMARK	Gadoversetamide	Linear
	ProHance	Gadoteridol	Macrocyclic
	Other, provide name:		

- 1.) The FDA has concluded that gadolinium is retained in the body and brain for a significantly longer time than previously recognized, especially for linear GBCAs. The health-related risks of this longer retention are not yet clearly established. However, the UW IRB expects researchers to provide a compelling justification for using a linear GBCA instead of a macrocyclic GBCA, to manage the risks associated with GBCAs.

Describe why it is important to use a GBCA with the MRI scan(s). Describe the dose that will be used and (if it is more than the standard clinical dose recommended by the manufacturer) why it is necessary to use a higher dose. If a linear GBCA will be used, explain why a macrocyclic GBCA cannot be used.

- 2.) Information for subjects. Confirm by checking this box that subjects will be provided with the FDA-approved Patient Medication Guide for the GBCA being used in the research or that the same information will be inserted into the consent form.

Confirmed

c. **MRI facility.** At which facility(ies) will the MRI scans occur? Check all that apply.

- UWMC Radiology/Imaging Services (the UWMC clinical facility)
- DISC Diagnostic Imaging Sciences Center (UWMC research facility)
- BMIC Biomolecular Imaging Center (South Lake Union research facility)
- Harborview Radiology/Imaging Services (the Harborview clinical facility)
- SCCA Imaging Services
- Northwest Diagnostic Imaging
- Other: identify in the text box below:

Personnel. For MRI scans that will be conducted at the DISC or BMIC research facilities: The role, qualifications, and training of individuals who will operate the scanner, administer the GBCA (if applicable), and/or insert and remove the IV catheter should be described in question **12.3**.

5.4 Data variables. Describe the specific data that will be obtained (including a description of the most sensitive items). Alternatively, a list of the data variables may be uploaded to **Zipline**.

OMC clinic outcomes data: report including the number of patients seen at OMC with a diagnosis of breast, ovarian, prostate, colon, and pancreatic cancer

OMC patients' Family History Questionnaire responses

OMC patients' identified data on clinical diagnosis and stage, pathology report features, and treatment options for patients with a diagnosis of breast, ovarian, prostate, colon, and pancreatic cancer

5.5 Data sources. For all types of data that will be accessed or collected for this research: Identify whether the data are being obtained from the subjects (or subjects' specimens) or whether they are being obtained from some other source (and identify the source).

If you have already provided this information in Question 5.1, you do not need to repeat the information here.

OMC clinic outcomes data: pulled from patients' clinical charts e.g. "referred for genetic counseling". Collected by OMC

Family History Questionnaire responses: filled out directly by patients then collected by OMC

OMC patients' identified data/relevant medical records: pulled from Epic. Collected by OMC

5.6 Identifiability of data and specimens. Answer these questions carefully and completely. This will allow HSD to accurately determine the type of review that is required and the relevant compliance requirements. Review the following definitions before answering the questions:

Access means to view or perceive data, but not to possess or record it. See, in contrast, the definition of "obtain".

Identifiable means that the identity of an individual is or may be readily (1) ascertained by the researcher or any other member of the study team from specific data variables or from a combination of data variables, or (2) associated with the information.

Direct identifiers are direct links between a subject and data/specimens. Examples include (but are not limited to): name, date of birth, medical record number, email or IP address, pathology or surgery accession number, student number, or a collection of data that is (when taken together) identifiable.

Indirect identifiers are information that links between direct identifiers and data/specimens. Examples: a subject code or pseudonym.

Key refers to a single place where direct identifiers and indirect identifiers are linked together so that, for example, coded data can be identified as relating to a specific person. Example: a master list that contains the data code and the identifiers linked to the codes.

Obtain means to possess or record in any fashion (writing, electronic document, video, email, voice recording, etc.) for research purposes and to retain for any length of time. This is different from **accessing**, which means to view or perceive data.

a. Will you or any members of your team have access to any direct or indirect identifiers?

Yes

→ If yes, describe which identifiers and for which data/specimens.

OMC will have access to all of their patients' identifiers as part of their standard processes of care. The SCCA study team will not have direct access to any direct or indirect identifiers unless sent to them by OMC.

No

→ If no, select the reason(s) why you (and all members of your team) will not have access to direct or indirect identifiers.

There will be no identifiers.

Identifiers or the key have been (or will have been) destroyed before access.

There is an agreement with the holder of the identifiers (or key) that prohibits the release of the identifiers (or key) to study team members under any circumstances.

This agreement should be available upon request from the IRB. Examples: a Data Use Agreement, Repository Gatekeeping form, or documented email.

There are written policies and procedures for the repository/database/data management center that prohibit the release of the identifiers (or identifying link). This includes situations involving an Honest Broker.

There are other legal requirements prohibiting the release of the identifiers or key. Describe them below.

b. Will you or any study team members obtain any direct or indirect identifiers?

Yes

→ If yes, describe which identifiers and for which data/specimens.

The study's research coordinator will obtain identifiers through OMC as included in the patients' medical records. This will include medical record number, first and last name, and date of birth.

No

→ If no, select the reason(s) why you (and all members of your team) will not obtain direct or indirect identifiers.

There will be no identifiers.

Identifiers or the key have been (or will have been) destroyed before access.

There will be an agreement with the holder of the identifiers (or key) that prohibits the release of the identifiers (or key) under any circumstances.

This agreement should be available upon request from the IRB. Examples: a Data Use Agreement, Repository Gatekeeping form, or documented email.

There are written policies and procedures for the repository/database/data management center that prohibit the release of the identifiers (or identifying link). This includes situations involving an Honest Broker.

There are other legal requirements prohibiting the release of the identifiers or key. Describe them below.

c. If any identifiers will be obtained, indicate how the identifiers will be stored (and for which data). NOTE: Do not describe the data security plan here – that information is requested in section 9.6.

Identifiers will be stored with the data. Describe the data to which this applies:

Identifiers and study data will be stored separately but a link will be maintained between the identifiers and the study data (for example, through the use of a code). Describe the data to which this applies:

This will apply to FHQ results as well as data on patients' clinical diagnosis and stage, pathology report features, and treatment options. The study's research coordinator will use a tracking sheet to document patient identification and their assigned participant ID, which will be stored in a private SCCA network J-drive folder.

Identifiers and study data will be stored separately, with no link between the identifiers and the study data. Describe the data to which this applies:

d. Research collaboration. Will individuals who provide coded information or specimens for the research also collaborate on other activities for this research? If yes, identify the activities and provide the name of the collaborator's institution/organization.

Examples include but are not limited to: (1) study, interpretation, or analysis of the data that results from the coded information or specimens; and (2) authorship on presentations or manuscripts related to this work.

Yes: The study's research coordinator will be involved in coordinating and organizing the bi-monthly conference meetings with the OMC provider subjects and SCCA study team. They will also be involved in the interpretation and analysis of the data that results from the coded information.

5.7 Protected Health Information (PHI). Will participants' identifiable PHI be accessed, obtained, used, or disclosed for any reason (for example, to identify or screen potential subjects, to obtain study data or specimens, for study follow-up) that does not involve the creation or obtaining of a Limited Data Set?

PHI is individually identifiable healthcare record information or clinical specimens from an organization considered a "covered entity" by federal HIPAA regulations, in any form or media, whether electronic, paper, or oral. You must answer yes to this question if the research involves identifiable health care records (e.g., medical, dental, pharmacy, nursing, billing, etc.), identifiable healthcare information from a clinical department repository, or observations or recordings of clinical interactions.

No → If no, skip the rest of this question; [go to question 5.8](#)

Yes → If yes, answer all of the questions below.

a. Describe the PHI and the reason for using it. *Be specific. For example, will any "free text" fields (such as physician notes) be accessed, obtained, or used?*

PHI will include patient's free text medical records regarding their clinical diagnosis and stage, pathology report features, and treatment options. It will also include their responses to the FHQ. This identified information will be accessed and obtained by OMC and the study's research coordinator at SCCA. The research coordinator will need access to the identified data in order to ensure seamless communication between OMC oncologists and the SCCA subject matter experts during meetings to identify and provide coaching on eligible patients for genetic counseling and testing.

b. Is any of the PHI located in Washington State?

No

Yes

c. Describe the pathway of how the PHI will be accessed or obtained, starting with the source/location and then describing the system/path/mechanism by which it will be identified, accessed, and copied for the research. *Be specific. For example: directly view records; search through a department's clinical database; submit a request to Leaf.*

OMC will directly access PHI through their medical records system. These will be compiled into patient packets as a single PDF for each, which will then be sent via secure email to the study's research coordinator at SCCA. The research coordinator will then securely store this information within a private SCCA network J-drive folder.

d. For which PHI will subjects provide HIPAA authorization before the PHI is accessed, obtained and/or used?

N/A. Subjects will not provide HIPAA authorization for any PHI

Confirm by checking the box that the UW Medicine [HIPAA Authorization](#) form maintained on the HSD website will be used to access, obtain, use, or disclose any UW Medicine PHI.

Confirmed

e. For which PHI will HIPAA authorization NOT be obtained from the subjects?

HIPAA authorization will not be obtained for any PHI from the OMC patient subjects. OMC has an established connection with SCCA as an SCCA affiliate site and already transfers patients' medical records to SCCA oncologists for review/second opinion. Transfer of PHI within the study will follow those same established guidelines.

Provide the following assurances by checking the boxes.

The minimum necessary amount of PHI to accomplish the purposes described in this application will be accessed, obtained and/or used.

The PHI will not be reused or disclosed to any other person or entity, except as required by law, for authorized oversight of the research study, or for other research for which the use or disclosure of PHI would be permitted.

The HIPAA "accounting for disclosures" requirement will be fulfilled, if applicable. See [UW Medicine Compliance Policy #104](#).

There will be reasonable safeguards to protect against identifying, directly or indirectly, any patient in any report of the research.

